3.3.1 Inclusion Criteria

1. Patients with locally advanced BCC of the head and neck, consisting of at least one histologically or cytologically confirmed lesion ≥ 20 mm in longest diameter that is considered to be inoperable or to have a medical contraindication to surgery, in the opinion of a Mohs dermatologic surgeon, head and neck surgeon, or plastic surgeon. Locally advanced disease is considered to include involved lymph nodes of the neck. A patient with regionally involved lymph nodes in the neck is considered eligible. The patient should be considered a candidate for radiotherapy and should not have medical contraindications to receipt of radiation therapy.

If a patient has distant metastatic spread of BCC (e.g., spread to distant areas outside the regional lymph nodes, clearly non contiguous areas of bone involvement, or distant metastasis to lung, brain, or other visceral organs), the patient should be considered as having distant metastasis and is not eligible.

Note: All lesions that the investigator proposes to follow as target lesions during the course of the study must have previously been histologically confirmed as BCC.

Acceptable contraindications to surgery include:

- BCC that has recurred in the same location after two or more surgical procedures and successful curative resection is deemed unlikely
- Complete surgical resection is not possible or is deemed excessively morbid (e.g. invasion into cranial nerves or skull base, proximity to brain, spinal canal, or orbit)

- Anticipated substantial morbidity and/or major deformity from surgery (e.g. removal of a major facial structure, such as nose, ear, eyelid, eye, or jaw; or requirement for upper limb amputation)
 - Medical contraindication to surgery
 - Patient refusal of surgery due to anticipated morbidity
 - Other conditions considered to be contraindicating must be discussed with Data Coordinator before enrolling the patient.
2. Prior radiation therapy is acceptable but there cannot be major overlap of the previously irradiated tissues with the new radiation treatment volumes anticipated to be delivered for the purposes of this protocol, in such a way that curative intent with radiation cannot be met. Furthermore, the total dose from all radiation delivered and expected to be delivered should not exceed the suggested dose constraints given for normal structures (see Section 5.2.7).
 3. Zubrod Performance Status 0-2
 4. Age ≥ 18 years of age

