5.2.5 Treatment Planning/Target Volumes

The definition of volumes will be in accordance with the 1993 ICRU Report #50, but the dose reporting and prescription are specified in Sections 5.2.

The Gross Tumor Volume (GTV) is defined as all known gross disease determined from imaging studies at presentation, clinical information, and physical examination findings. The GTV should encompass any area of disease visible or palpable at post-induction restaging and any areas involved on the initial imaging prior to induction, even if the area has responded to the drug. Grossly positive lymph nodes are defined as any lymph nodes > 1 cm in shortest dimension or nodes with a necrotic center. It is strongly encouraged that the radiation oncologist outline the radiologic extent of the primary tumor and any involved nodes along with a radiologist. Whenever possible, it is recommended that the diagnostic-quality images be fused to the planning CT scan image dataset to more accurately define the GTV as it existed prior to induction with vismodegib. To further subdivide the GTV, gross disease at the primary site may be designated as GTV-P and clinically involved gross lymph nodes may be designated GTV-N. In situations where the patient underwent surgical biopsy or surgery prior to radiation therapy, the GTV is defined as the residual gross disease thought to remain following the surgery.

The Clinical Target Volume (CTV): See Sections 5.2 for delineation details.

For patients without complete surgical resection: In terms of the GTV (GTV-P and GTV-N), a margin of 5 mm should be given circumferentially around the GTV (GTV-P and GTV-N) and this volume will be called the CTV1 (CTV1-P and CTV1-N). This margin can be reduced to as low as 1 mm for tumors in close proximity to critical structures, e.g., tumors next to the spinal cord or brain.

For regions deemed to be at high risk for microscopic disease, the treating radiation oncologist should delineate all potential routes of spread for primary and nodal GTVs. This is known as CTV for subclinical disease or CTV2. Delineation and treatment of CTV2 is optional and based on the judgment of the study investigators.

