6.1.1 Pretreatment Period

6.1.1.1 Screening Assessments

The Screening procedures and assessments must be completed within 14 days of the Day 1 Visit unless otherwise noted.

- Physical examination - The initial complete physical examination should include evaluation of the head, eyes, ears, nose and throat (HEENT); cardiovascular, dermatological, musculoskeletal, respiratory, gastrointestinal, and neurological systems. Height and weight will also be recorded.
- Vital signs
- Complete medical history – can be done within 28 days of Day 1
- Baseline conditions assessment
- Documentation of disease assessment - Assessments should include an evaluation of all sites of disease. Patients will undergo tumor assessments per RECIST version 1.1 tumor response criteria. Can be done within 28 days of Day 1
- Performance status
- Skindex-16 questionnaire
- History of prior treatments and any residual toxicity relating to prior treatment
- Baseline medications taken within 28 days of Day 1

- Laboratory assessments
 - Hematology (hemoglobin, hematocrit, platelet count, RBC count, WBC count, percent and absolute differential count [neutrophils, bands, eosinophils, lymphocytes, monocytes, basophils, other cells])
 - Serum chemistries (sodium, potassium, chloride, bicarbonate, glucose, BUN, creatinine, calcium, alkaline phosphatase, magnesium, total bilirubin, albumin, total protein, ALT, AST, and as clinically indicated; LDH, and phosphorus)
 - Pregnancy test: All women of childbearing potential (including those who have had a tubal ligation) will have a serum pregnancy test at screening, within 7 days of Day 1.
 - Urine or serum pregnancy tests will be performed every 4 weeks at specified subsequent visits. If a urine pregnancy test is positive, it must be confirmed by a serum pregnancy test.
 - Urinalysis
- Imaging (CT or MRI) of primary tumor region and any involved regional lymph nodes for tumor assessment. Can be done within 28 days of Day 1
 - Note: The CT scan with contrast or an MRI with gadolinium must be done unless medically contraindicated. The MRI or CT scan must encompass the skull base and/or upper mediastinum if those areas are involved. If locally advanced BCC lesions with a RECIST-measurable component are identified, the same imaging modality used at baseline must be used throughout the study.
- Chest x-ray or chest CT scan, or CT of chest and abdomen – can be done within 28 days of Day 1
- For externally visible tumors

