7.2 Antitumor Effect – Solid Tumors

Response and progression in this study will be evaluated using the new international criteria proposed by the Response Evaluation Criteria in Solid Tumors ([RECIST](#)) Committee [JNCI 92(3):205-216, 2000]. Assessments should include an evaluation of all sites of disease. Patients will undergo tumor assessments per RECIST tumor response criteria. Screening digital photographs of visible portions of the lesions may be taken any time from the start of screening until just prior to dosing on Day 1. Tumor measurements will be performed measuring the maximal diameter as the maximal extent of tumor plus any adjacent or underlying ulceration. Any tumors which were included in the original assessment as either a primary involved site or involved regional lymph node must be measured.

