7.2.1.2 Disease Parameters

Measurable disease

Measurable disease is defined as lesions (or tumors) that can be accurately measured in at least one dimension (longest diameter to be recorded) with a minimum size of 10mm by CT scan (irrespective of scanner type) and MRI (no less than double the slice thickness and a minimum of 10mm), 10mm caliper measurement by clinical exam (when superficial), and/or 20mm by chest X-ray (if clearly defined and surrounded by aerated lung).

Tumor measurements will be performed measuring the maximal diameter as the maximal extent of tumor plus any adjacent or underlying ulceration. All tumor measurements will be recorded in millimeters or decimal fractions of centimeters. Previously irradiated lesions are considered non-measurable except in cases of documented progression of the lesion since the completion of radiation therapy.

Target lesions

All measurable lesions up to a maximum of 5 lesions total (and a maximum of two lesions per organ) representative of all involved organs should be identified as target lesions and recorded and measured at baseline. Target lesions will be selected on the basis of their size (lesions with the longest diameter) and their suitability for accurate repeated measurements (either by imaging techniques or clinically). A sum of the longest diameter (LD) for all target lesions will be calculated and reported as the baseline sum LD. The baseline sum LD will be used as reference by which to characterize the objective tumor response.

Non-measurable disease

Non-measurable disease is all other lesions (or sites of disease), including small lesions (longest diameter <20 mm with conventional techniques or < 10 mm using spiral CT scan). Leptomeningeal disease, ascites, pleural or pericardial effusion, inflammatory breast disease, lymphangitic involvement of skin or lung, abdominal masses/abdominal organomegaly identified by physical exam that is not measurable by reproducible imaging techniques are all non-measurable.

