7.2.1.4 Response Criteria

Evaluation of Target Lesions

Complete Response (CR)

Disappearance of all target lesions in the irradiated PTV, determined by two separate observations conducted not less than 4 weeks apart. Any pathological lymph nodes (whether target or non-target) must have reduction in short axis to <10 mm (the sum may not be “0” if there are target nodes). There can be no appearance of new lesions in irradiated PTV.

Partial Response (PR)

At least a 30% decrease in the sum of the longest diameter (LD) of target lesions in the irradiated PTV, taking as reference the baseline sum LD. There can be no appearance of new lesions in irradiated PTV.

Progressive Disease (PD)

At least a 20% increase in the sum of the SLD of target lesions, taking as reference the smallest sum SLD recorded since the treatment started and minimum 5 mm increase over the nadir, or the appearance of one or more new lesions in the irradiated PTV.

Stable Disease (SD)

Neither sufficient shrinkage to qualify for PR nor sufficient increase to qualify for PD, taking as reference the smallest sum LD since the treatment started.

Evaluation of Best Overall Response

The best overall response is the best response recorded from the start of the treatment until disease progression/recurrence (taking as reference for PD the smallest measurements recorded since the treatment started). The patient's best response assignment will depend on the achievement of both measurement and confirmation criteria.

Table 7.1 Response Criteria

Target Lesions	Non-Target Lesions	New Lesions	Overall Response	Best Response for this Category Also Requires
CR	CR	No	CR	> 4 weeks confirmation
CR	Non-CR/ Non-PD	No	PR	> 4 weeks confirmation
PR	Non-PD	No	PR	
SD	Non-PD	No	SD	documented at least once > 4 weeks from baseline
PD	Any	Yes or No	PD	no prior SD, PR or CR
Any	PD*	Yes or No	PD	
Any	Any	Yes	PD	

* In exceptional circumstances, unequivocal progression in non-target lesions may be accepted as disease progression. These circumstances should be discussed with the Principal Investigators.

Duration of Response

Duration of overall response

The duration of overall response is measured from the time measurement criteria are met for CR or PR (whichever is first recorded) until the first date that recurrent or PD is objectively

documented (taking as reference for PD the smallest measurements recorded since the treatment started).

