8.3 Determination of Sample Size and Accrual Rate

8.3.1 Sample Size and Power Estimate

The sample size for this single-arm phase II study is based upon the anticipated degree of improvement in the primary clinical hypothesis (i.e. local-regional control rate) at 12 months after completing all protocol treatment. The null hypothesis is that 60% of patients treated may achieve local-regional control after treatment on the study. Patients treated for advanced-stage

nonmelanomatous skin cancers typically achieve 50-60% local-regional control with radiation therapy alone. The alternative hypothesis is that 80% of the patients will obtain local-regional control at 12 months from the end of protocol therapy. This goal for local-regional control is justifiable as the current study includes radiation therapy, which is known to be effective against advanced BCC, in combination with vismodegib, also known to have high efficacy against BCC when administered alone.

Sample Size Justification: With accrual of 24 evaluable patients, this test will have 81% power to detect an increase in the overall proportion of patients achieving local-regional control assuming a directional level of significance of 0.10 based upon a one sample exact binomial test. It is anticipated that accrual will be completed in 12-18 months, with each patient treated for approximately 5.5 months and then followed for 12 months after completing protocol therapy. The total study duration is expected to be about 3 years.

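### Section 7.2 sums nodal target lesions by longest diameter but decides nodal CR by short axis, so a node that changes shape can be misclassified either way in the primary endpoint, and section 7.3 uses yet another rule

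*Combined protocol and SAP*

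**What the plan says.** - **Eligibility (3.3.1):** "A patient with regionally involved lymph nodes in the neck is considered eligible". The same section requires BCC histology for any lesion that is to be followed as a target.
- **The sum (7.2.1.2):** "A sum of the longest diameter (LD) for all target lesions will be calculated and reported as the baseline sum LD". Nothing separate is said about nodes.
- **Response rules (7.2.1.4):** for CR, pathological nodes "must have reduction in short axis to <10 mm". PR is a fall of 30% or more in the longest-diameter (LD) sum. PD is a rise of at least 20% and at least 5 mm over the nadir, or a new lesion in the irradiated PTV. The PD rule names its sum SLD, an abbreviation that is not defined.
- **Gross nodal disease (5.2.5):** "Grossly positive lymph nodes are defined as any lymph nodes > 1 cm in shortest dimension".
- **RECIST version:** section 6.1.1.1 says "Patients will undergo tumor assessments per RECIST version 1.1 tumor response criteria", and the Abstract also names version 1.1. Section 7.2 instead cites "JNCI 92(3):205-216, 2000".
- **Primary endpoint:** section 8.2 requires CR or PR without PD in the PTV and refers to section 7.2 for PD. Section 8.5 counts patients in CR or PR at 12 months.
- **Failure patterns (7.3):** relapse is tumor that reappears after CR. Progression is a rise of more than 20% in the product of two perpendicular diameters. The endpoint does not refer to this section.

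**The concern.** The endpoint is local-regional and node-positive patients can enter, so nodes are part of it. The protocol uses the shortest dimension to say whether a node is diseased and whether it has normalized. Within section 7.2, however, that dimension does not enter PR, nadir or PD. A node can therefore meet the CR rule while its longest diameter has hardly moved, and can later thicken without raising the sum enough for PD.

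The error can go both ways. A nodal relapse may be scored as control. A normalized but elongated node may hold a genuine response at SD, which the endpoint counts as failure. The two RECIST citations do not settle which axis applies, and section 7 requires no central imaging review, so each site would have to resolve the conflict itself.

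**Working it through.** **1. The plan's own figure.** Section 8.3.1 gives 24 evaluable patients, a null of 60%, an alternative of 80%, "assuming a directional level of significance of 0.10 based upon a one sample exact binomial test", and states "With accrual of 24 evaluable patients, this test will have 81% power". With X binomial(24, p):

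- P(X ≥ 17 | 0.60) = 0.192 and P(X ≥ 18 | 0.60) = 0.096, so the cutoff is 18 of 24.
- P(X ≥ 18 | 0.80) = 0.811, so the stated 81% is reproduced.

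**2. The section 7.2 rules.** Let B be the baseline sum, N the nadir and S the current sum. PR requires (B − S)/B ≥ 30%. PD requires (S − N)/N ≥ 20% and S − N ≥ 5 mm.

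**3. Regrowth after normalizing.** The documents give no node sizes, so all sizes here are assumed. In each row the primary has disappeared and the node was below 10 mm in short axis at response.

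| Node, LD × short axis (mm) | LD sum (7.2) | Short-axis sum | Product (7.3) |
|---|---|---|---|
| 25×9 to 26×18 | +1 mm, +4%: not PD | +9 mm, +100%: PD | 225 to 468, +108%: progression |
| 14×8 to 17×14 | +3 mm, +21%: not PD | +6 mm, +75%: PD | 112 to 238, +112.5%: progression |
| 12×8 to 16×11 | +4 mm, +33%: not PD | +3 mm, +37.5%: not PD | 96 to 176, +83%: progression |

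Status under section 7.2:

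- Row 1: baseline is a 20 mm primary plus a node of LD 25 mm, so B = 45 and (45 − 26)/45 = 42% below baseline.
- Rows 2 and 3: baseline is a 40 mm primary plus a 24×16 mm node, so B = 64, and the sums are (64 − 17)/64 = 73% and (64 − 16)/64 = 75% below baseline.

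All three are PR and count as control.

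**4. A response held back.** Primary 20 to 8 mm; two nodes, each 30×15 to 28×9 mm.

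- LD sum: 20 + 30 + 30 = 80 to 8 + 28 + 28 = 64 mm, −20%: SD, counted as failure.
- Short axis for nodes: 20 + 15 + 15 = 50 to 8 + 9 + 9 = 26 mm, −48%: PR.

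This needs residual primary disease. Had the primary gone, nodes below 10 mm would meet the target-lesion CR rule whatever their length.

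**5. How much the axis itself does.** Take a node that keeps its shape (LD/short axis 1.5), is 8 mm in short axis at response, and is the only disease left.

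- LD sum: 12 mm, PD at 12 + 5 = 17 mm, which is a short axis of 17/1.5 = 11.3 mm.
- Short-axis sum: PD at 8 + 5 = 13.0 mm.

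So the LD sum is the earlier one when shape is preserved. The axis alone decides rows 1 and 2, where the node rounds out. Row 3 is missed on both axes because of the 5 mm floor.

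**6. Effect on the test.** One patient is 1/24 = 4.2 points. At 18/24, p = 0.096 and the null is rejected; at 17/24, p = 0.192 and it is not. If a net share of 2%, 5% or 10% of patients (assumed) were wrongly counted as controlled on top of a true 60%, P(X ≥ 18) would be 0.134, 0.211 or 0.389.

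**The case against.** **Section 7.3 catches these nodes.** It does: its product rule brings in the second diameter and calls all three regrowth cases progression. The absence of short axis from PR and PD is therefore a feature of section 7.2, not of the whole protocol. But section 8.2 sends the reader to 7.2 for PD, so the effect is a conflict between two sections, with the less sensitive rule attached to the endpoint.

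**RECIST 1.1 is named, so it governs.** The section that defines response writes out its own sum and cites the 2000 paper. Naming version 1.1 elsewhere does not override that.

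**The examples are built to fail.** Partly true. They need a node that changes shape, and the missed relapse also needs the LD sum to stay at least 30% below baseline, here because the primary vanished. If the node were the only target, with an assumed baseline LD of 30 mm, 26 mm would be −13%: SD, hence failure and not control.

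**A long but normal node could be picked as a target.** A reader might infer this from the 10 mm size rule in 7.2.1.2. The histology requirement in 3.3.1 rules it out: a target must already be confirmed as BCC.

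**It will rarely happen.** Possibly. Section 1.1.1 calls metastatic BCC extremely rare, but that describes BCC overall. The documents do not say how many node-positive patients to expect in this locally advanced population.

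**Conclusion.** The point holds in a limited form. For nodal target lesions section 7.2 is inconsistent with itself and with section 7.3, and this is a stated rule that is wrong as written rather than a detail left out. A biopsy-confirmed target node that rounds out after normalizing can avoid PD and, if the LD sum is still at least 30% below baseline, be counted as local-regional control. Elongated, normalized nodes with residual primary disease can turn a response into a failure.

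The size for the trial as a whole cannot be stated: node dimensions are assumed and the share of node-positive patients is unknown. A reader might infer that the sample size is wrong or that the type I error is inflated. The documents support neither. The 81% power is correct, the inflated error rates rest on assumed net shares in one direction, and misclassification can run the other way too. What can be said is that one reclassified patient at the boundary changes the conclusion. The protocol should be corrected; confidence is moderate because the frequency is unknown.

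**What to change.** 1. Name RECIST 1.1 once as the governing version and remove the 2000 citation from section 7.2.
2. In 7.2.1.2 and 7.2.1.4, replace both sum LD and SLD with one defined sum of diameters: longest diameter for non-nodal targets and short axis for nodal targets. Use it for baseline, PR, nadir and PD. Short axis is the dimension that the protocol already uses for nodal CR and gross nodal disease.
3. State how the primary endpoint scores a node that met the below-10 mm rule and returns to 10 mm or more in short axis, including when the increase is under 5 mm. Without this, regrowth from 8 to 11 mm is still missed.
4. Reconcile section 7.2 with the relapse and progression definitions in 7.3, and say which governs the endpoint.

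The cost is protocol wording and a CRF field. The scans are already scheduled, and short axis must already be read for CR. There is one downside: for nodes that keep their shape, a short-axis sum can reach PD slightly later (13.0 against 11.3 mm in the case worked above), which is a further reason for item 3.

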7.2.1.3 Methods for Evaluation of Measurable Disease

All measurements will be taken and recorded in metric notation using a ruler or calipers. All baseline evaluations will be performed as closely as possible to the beginning of treatment and never more than 28 days before the beginning of the treatment.

The same method of assessment and the same technique will be used to characterize each identified and reported lesion at baseline and during follow-up. Imaging-based evaluation is preferred to evaluation by clinical examination when both methods have been used to assess the antitumor effect of a treatment.

Conventional CT and MRI

CT or MRI scans will be performed of the primary tumor site and any regionally involved nodal regions. These imaging studies will be performed with contrast (iodinated or gadolinium) unless medically contraindicated. These techniques should be performed with cuts of 10 mm or less in slice thickness contiguously. Spiral CT should be performed using a 5 mm contiguous reconstruction algorithm. This applies to tumors of the chest, abdomen, and pelvis.

